8.1.2. Eliciting Adverse Event Information

The investigator is to record on the CRF all directly observed AEs and all AEs spontaneously reported by the study patient. In addition, each study patient will be questioned about the occurrence of AEs in a non-leading manner.

8.1.3. Withdrawal from the Study Due to Adverse Events (see also the [Patient Withdrawal](#) section)

Withdrawal due to AEs should be distinguished from withdrawal due to other causes, according to the definition of AE noted below, and recorded on the CRF.

When a patient withdraws from the study because of an SAE, the SAE must be recorded on the CRF and reported, as appropriate, on the CT SAE Report Form, in accordance with the [Requirements](#) section above.

8.1.4. Time Period for Collecting AE/SAE Information

The time period for actively eliciting and collecting AEs and SAEs (“active collection period”) for each patient begins from the time the patient provides informed consent, which is obtained before the patient’s participation in the study (ie, before undergoing any study-related procedure and/or receiving investigational product), through and including a minimum of 28 calendar days; except as indicated below after the last administration of the investigational product.

Part 2 Only: During the long-term follow-up period in this study for survival, only SAEs will be actively elicited and collected after completion of the active collection period described above. The SAEs identified during long-term follow-up will be reported to Pfizer Safety on the CT SAE Report Form only if considered reasonably related to the study intervention.

For patients who are screen failures, the active collection period ends when screen failure status is determined.

8.1.4.1. Reporting SAEs to Pfizer Safety

All SAEs occurring in a patient during the active collection period are reported to Pfizer Safety on the CT SAE Report Form.

SAEs occurring in a patient after the active collection period has ended are reported to Pfizer Safety if the investigator becomes aware of them; at a minimum, all SAEs that the investigator believes have at least a reasonable possibility of being related to investigational product must be reported to Pfizer Safety.

Follow up by the investigator continues throughout and after the active collection period and until the event or its sequelae resolve or stabilize at a level acceptable to the investigator, and Pfizer concurs with that assessment.

If a patient begins a new anticancer therapy, SAEs occurring during the above-indicated active collection period must still be reported to Pfizer Safety irrespective of any intervening treatment.

8.1.4.2. Recording Non-serious AEs and SAEs on the CRF

During the active collection period, both non-serious AEs and SAEs are recorded on the CRF.

Follow-up by the investigator may be required until the event or its sequelae resolve or stabilize at a level acceptable to the investigator, and Pfizer concurs with that assessment.

If a patient begins a new anticancer therapy, the recording period for non-serious AEs ends at the time the new treatment is started; however, SAEs must continue to be recorded on the CRF during the above-indicated active collection period.

8.1.5. Causality Assessment

The investigator's assessment of causality must be provided for all AEs (serious and non-serious); the investigator must record the causal relationship on the CRF, and report such an assessment in accordance with the SAE reporting requirements, if applicable. An investigator's causality assessment is the determination of whether there exists a reasonable possibility that the investigational product caused or contributed to an AE; generally, the facts (evidence) or arguments to suggest a causal relationship should be provided. If the investigator does not know whether or not the investigational product caused the event, then the event will be handled as "related to investigational product" for reporting purposes, as defined by the sponsor. If the investigator's causality assessment is "unknown but not related" to investigational product, this should be clearly documented on study records.

In addition, if the investigator determines that an SAE is associated with study procedures, the investigator must record this causal relationship in the source documents and CRF, and report such an assessment in the dedicated section of the CT SAE Report Form and in accordance with the SAE reporting requirements.

8.1.6. Sponsor's Reporting Requirements to Regulatory Authorities

AE reporting, including suspected unexpected serious adverse reactions, will be carried out in accordance with applicable local regulations.

8.2. Definitions

8.2.1. Adverse Events

An AE is any untoward medical occurrence in a study patient administered a product or medical device; the event need not necessarily have a causal relationship with the treatment or usage. Examples of AEs include, but are not limited to:

- Abnormal test findings;
- Clinically significant signs and symptoms;

- Changes in physical examination findings;
- Hypersensitivity;
- Drug abuse;
- Drug dependency.

Additionally, AEs may include signs and symptoms resulting from:

- Drug overdose;
- Drug withdrawal;
- Drug misuse;
- Drug interactions;
- Extravasation;
- Exposure during pregnancy (EDP);
- Exposure via breastfeeding;
- Medication error;
- Occupational exposure.

Worsening of signs and symptoms of the malignancy under study should be recorded as AEs in the appropriate section of the CRF. Disease progression assessed by measurement of malignant lesions on radiographs or other methods should not be reported as AEs.

8.2.2. Abnormal Test Findings

Abnormal objective test findings should be recorded as AEs when any of the following conditions are met:

- Test result is associated with accompanying symptoms; and/or
- Test result requires additional diagnostic testing or medical/surgical intervention; and/or
- Test result leads to a change in study dosing (outside of any protocol-specified dose adjustments) or discontinuation from the study, significant additional concomitant drug treatment, or other therapy; and/or
- Test result is considered to be an AE by the investigator or sponsor.

Merely repeating an abnormal test, in the absence of any of the above conditions, does not constitute an AE. Any abnormal test result that is determined to be an error does not require recording as an AE.

8.2.3. Serious Adverse Events

A serious adverse event is any untoward medical occurrence at any dose that:

- Results in death;
- Is life-threatening (immediate risk of death);
- Requires inpatient hospitalization or prolongation of existing hospitalization;
- Results in persistent or significant disability/incapacity (substantial disruption of the ability to conduct normal life functions);
- Results in congenital anomaly/birth defect.

Or that is considered to be:

- An important medical event.

Medical and scientific judgment is exercised in determining whether an event is an important medical event. An important medical event may not be immediately life-threatening and/or result in death or hospitalization. However, if it is determined that the event may jeopardize the patient or may require intervention to prevent one of the other AE outcomes, the important medical event should be reported as serious.

Examples of such events are intensive treatment in an emergency room or at home for allergic bronchospasm; blood dyscrasias or convulsions that do not result in hospitalization; or development of drug dependency or drug abuse.

Progression of the malignancy under study (including signs and symptoms of progression) should not be reported as an SAE unless the outcome is fatal within the active collection period. Hospitalization due to signs and symptoms of disease progression should not be reported as an SAE. If the malignancy has a fatal outcome during the study or within the active collection period, then the event leading to death must be recorded as an AE on the CRF, and as an SAE with Common Terminology Criteria for Adverse Events (CTCAE) Grade 5 (see the [Severity Assessment](#) section).

8.2.4. Hospitalization

Hospitalization is defined as any initial admission (even less than 24 hours) in a hospital or equivalent healthcare facility, or any prolongation of an existing admission. Admission also includes transfer within the hospital to an acute/intensive care unit (eg, from the psychiatric wing to a medical floor, medical floor to a coronary care unit, or neurological floor to a

tuberculosis unit). An emergency room visit does not necessarily constitute a hospitalization; however, the event leading to the emergency room visit is assessed for medical importance.

Hospitalization does not include the following:

- Rehabilitation facilities;
- Hospice facilities;
- Respite care (eg, caregiver relief);
- Skilled nursing facilities;
- Nursing homes;
- Same-day surgeries (as outpatient/same-day/ambulatory procedures).

Hospitalization or prolongation of hospitalization in the absence of a precipitating clinical AE is not in itself an SAE. Examples include:

- Admission for treatment of a preexisting condition not associated with the development of a new AE or with a worsening of the preexisting condition (eg, for workup of a persistent pretreatment laboratory abnormality);
- Social admission (eg, patient has no place to sleep);
- Administrative admission (eg, for yearly physical examination);
- Protocol-specified admission during a study (eg, for a procedure required by the study protocol);
- Optional admission not associated with a precipitating clinical AE (eg, for elective cosmetic surgery);
- Hospitalization for observation without a medical AE;
- Preplanned treatments or surgical procedures. These should be noted in the baseline documentation for the entire protocol and/or for the individual patient;
- Admission exclusively for the administration of blood products.

Diagnostic and therapeutic noninvasive and invasive procedures, such as surgery, should not be reported as SAEs. However, the medical condition for which the procedure was performed should be reported if it meets the definition of an SAE. For example, an acute appendicitis that begins during the reporting period should be reported if the SAE requirements are met, and the resulting appendectomy should be recorded as treatment of the AE.

8.3. Severity Assessment

GRADE	Clinical Description of Severity
0	No change from normal or reference range (This grade is not included in the Version 4.03 CTCAE document but may be used in certain circumstances.)
1	MILD adverse event
2	MODERATE adverse event
3	SEVERE adverse event
4	LIFE-THREATENING consequences; urgent intervention indicated
5	DEATH RELATED TO adverse event

Note the distinction between the severity and the seriousness of an AE. A severe event is not necessarily an SAE. For example, a headache may be severe (interferes significantly with the patient's usual function) but would not be classified as serious unless it met one of the criteria for SAEs, listed above.

8.4. Special Situations

8.4.1. Potential Cases of Drug-Induced Liver Injury

Humans exposed to a drug who show no sign of liver injury (as determined by elevations in transaminases) are termed "tolerators," while those who show transient liver injury, but adapt are termed "adaptors." In some patients, transaminase elevations are a harbinger of a more serious potential outcome. These patients fail to adapt and therefore are "susceptible" to progressive and serious liver injury, commonly referred to as drug-induced liver injury (DILI). Patients who experience a transaminase elevation above 3 times the upper limit of normal (\times ULN) should be monitored more frequently to determine if they are an "adaptor" or are "susceptible."

In the majority of DILI cases, elevations in aspartate aminotransferase (AST) and/or alanine aminotransferase (ALT) precede total bilirubin (TBili) elevations ($>2 \times \text{ULN}$) by several days or weeks. The increase in TBili typically occurs while AST/ALT is/are still elevated above $3 \times \text{ULN}$ (ie, AST/ALT and TBili values will be elevated within the same lab sample). In rare instances, by the time TBili elevations are detected, AST/ALT values might have decreased. This occurrence is still regarded as a potential DILI. Therefore, abnormal elevations in either AST OR ALT in addition to TBili that meet the criteria outlined below are considered potential DILI (assessed per Hy's law criteria) cases and should always be considered important medical events, even before all other possible causes of liver injury have been excluded.

The threshold of laboratory abnormalities for a potential DILI case depends on the patient's individual baseline values and underlying conditions. Patients who present with the following laboratory abnormalities should be evaluated further as potential DILI (Hy's law) cases to definitively determine the etiology of the abnormal laboratory values:

- Patients with AST/ALT and TBili baseline values within the normal range who subsequently present with AST **OR** ALT values $>3 \times \text{ULN}$ AND a TBili value $>2 \times \text{ULN}$ with no evidence of hemolysis and an alkaline phosphatase value $<2 \times \text{ULN}$ or not available;
- For patients with baseline AST **OR** ALT **OR** TBili values above the ULN, the following threshold values are used in the definition mentioned above, as needed, depending on which values are above the ULN at baseline:
 - Preexisting AST or ALT baseline values above the normal range: AST or ALT values >2 times the baseline values AND $>3 \times \text{ULN}$; or $>8 \times \text{ULN}$ (whichever is smaller).
 - Preexisting values of TBili above the normal range: TBili level increased from baseline value by an amount of at least $1 \times \text{ULN}$ **or** if the value reaches $>3 \times \text{ULN}$ (whichever is smaller).

Rises in AST/ALT and TBili separated by more than a few weeks should be assessed individually based on clinical judgment; any case where uncertainty remains as to whether it represents a potential Hy's law case should be reviewed with the sponsor.

The patient should return to the investigator site and be evaluated as soon as possible, preferably within 48 hours from awareness of the abnormal results. This evaluation should include laboratory tests, detailed history, and physical assessment.

In addition to repeating measurements of AST and ALT and TBili for suspected Hy's law cases, additional laboratory tests should include albumin, creatine kinase (CK), direct and indirect bilirubin, gamma-glutamyl transferase (GGT), prothrombin time (PT)/international normalized ratio (INR), and alkaline phosphatase. Consideration should also be given to drawing a separate tube of clotted blood and an anticoagulated tube of blood for further

testing, as needed, for further contemporaneous analyses at the time of the recognized initial abnormalities to determine etiology. A detailed history, including relevant information, such as review of ethanol, acetaminophen (either by itself or as a coformulated product in prescription or over-the-counter medications), recreational drug, supplement (herbal) use and consumption, family history, sexual history, travel history, history of contact with a jaundiced person, surgery, blood transfusion, history of liver or allergic disease, and potential occupational exposure to chemicals, should be collected. Further testing for acute hepatitis A, B, C, D, and E infection and liver imaging (eg, biliary tract), total bile acids, and collection of serum samples for acetaminophen/paracetamol drug and/or protein adduct levels may be warranted.

All cases demonstrated on repeat testing as meeting the laboratory criteria of AST/ALT and TBili elevation defined above should be considered potential DILI (Hy's law) cases if no other reason for the liver function test (LFT) abnormalities has yet been found. **Such potential DILI (Hy's law) cases are to be reported as SAEs, irrespective of availability of all the results of the investigations performed to determine etiology of the LFT abnormalities.**

A potential DILI (Hy's law) case becomes a confirmed case only after all results of reasonable investigations have been received and have excluded an alternative etiology.

8.4.2. Exposure to the Investigational Product During Pregnancy or Breastfeeding, and Occupational Exposure

Exposure to the investigational product under study during pregnancy or breastfeeding and occupational exposure are reportable to Pfizer Safety within 24 hours of investigator awareness.

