 - Progressed during treatment or within 12 months of completion of adjuvant therapy with an aromatase inhibitor if postmenopausal, or tamoxifen if pre- or peri-menopausal, or
 - Progressed while on or within 1 month after the end of prior aromatase inhibitor therapy for advanced/metastatic breast cancer if postmenopausal, or prior endocrine treatment for advanced/metastatic breast cancer if pre- or peri-menopausal.
2. All patients must be refractory to or intolerant of existing therapies known to provide clinical benefit for their condition (Part 1 only).
 3. Female patients age ≥ 18 years (all Parts) or male patients ≥ 18 years (Part 1A and Part 1C) and/or ≥ 20 years in Japan.
 4. Eastern Cooperative Oncology Group (ECOG) Performance Status (PS) 0 or 1.
 5. Adequate Bone Marrow Function, including:
 - a. Absolute Neutrophil Count (ANC) $\geq 1,500/\text{mm}^3$ or $\geq 1.5 \times 10^9/\text{L}$;
 - b. Platelets $\geq 100,000/\text{mm}^3$ or $\geq 100 \times 10^9/\text{L}$;
 6. Hemoglobin ≥ 9 g/dL.
 7. Adequate Renal Function, defined as:
 - a. Estimated creatinine clearance ≥ 60 mL/min for Part 1 and ≥ 50 mL/min for Part 2 as calculated using the method standard for the institution. In equivocal

cases, a 24-hour urine collection test can be used to estimate the creatinine clearance more accurately.

8. Adequate Liver Function, including:
 - a. Total serum bilirubin ≤ 1.5 x ULN unless the patient has documented Gilbert syndrome;
 - b. Aspartate and alanine aminotransferase (AST and ALT) ≤ 2.5 x ULN; ≤ 5.0 x ULN if there is liver involvement by the tumor;
 - c. Alkaline phosphatase ≤ 2.5 x ULN (≤ 5 x ULN in case of bone or liver metastasis).
9. Resolved acute effects of any prior therapy to baseline severity or CTCAE Grade ≤ 1 except for adverse events (AEs) not constituting a safety risk by investigator judgment.
10. For Part 2 only, measurable disease as defined by RECIST 1.1 is required.
11. Serum pregnancy test (for females of childbearing potential) negative at screening.

Female patients of nonchildbearing potential must meet at least 1 of the following criteria and will not require a serum pregnancy test at screening:

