For each event, the investigator must pursue and obtain adequate information both to determine the outcome and to assess whether it meets the criteria for classification as an SAE (see the [Serious Adverse Events](#) section below). In addition, the investigator may be requested by Pfizer Safety to obtain specific follow-up information in an expedited fashion. This information is more detailed than that recorded on the CRF. In general, this will include a description of the event in sufficient detail to allow for a complete medical assessment of the case and independent determination of possible causality. Any information relevant to the event, such as concomitant medications and illnesses, must be provided. In the case of a patient death, a summary of available autopsy findings must be submitted as soon as possible to Pfizer Safety. Any pertinent additional information must be reported on the CT SAE Report Form; additional source documents (eg, medical records, CRF, laboratory data) are to be sent to Pfizer Safety **ONLY** upon request.

As part of ongoing safety reviews conducted by the sponsor, any non-serious AE that is determined by the sponsor to be serious will be reported by the sponsor as an SAE. To assist in the determination of case seriousness, further information may be requested from the investigator to provide clarity and understanding of the event in the context of the clinical study.

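### Section 8.4.1 adjusts the potential Hy's law limits for raised baseline AST/ALT and bilirubin but keeps ALP <2 x ULN fixed, although criterion 8c admits patients who already exceed it

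*Protocol*

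**What the plan says.** Protocol Section 8.4.1 opens its threshold rules by saying that they depend on the patient's "individual baseline values and underlying conditions". With normal baseline AST/ALT and TBili, a potential case needs AST or ALT >3 x ULN and TBili >2 x ULN, "with no evidence of hemolysis and an alkaline phosphatase value" below 2 x ULN or not available. If AST, ALT or TBili is above normal at baseline, "the following threshold values are used in the definition mentioned above":

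- AST/ALT: more than twice baseline and >3 x ULN, or >8 x ULN, whichever is smaller.
- TBili: a rise of at least 1 x ULN, or a value >3 x ULN, whichever is smaller.

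No substitute is given for ALP.

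Inclusion criterion 8c (Section 4.1) admits ALP up to 2.5 x ULN, raised to 5 "x ULN in case of bone or liver metastasis".

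Later in Section 8.4.1, cases shown on repeat testing as "meeting the laboratory criteria of AST/ALT and TBili elevation defined above" count as potential cases and are reported as SAEs "if no other reason for the liver function test (LFT) abnormalities has yet been found". A case is confirmed only once other causes have been excluded. A confirmed case is a DLT (Section 3.1.6) and requires discontinuation (note to Table 3).

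SAP Section 9.2.3.2 tabulates the worst grade for each laboratory test separately.

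**The concern.** The definition has three numerical conditions. Two are adapted to patients who enter with abnormal values. The third is not, although criterion 8c expects bone or liver metastasis to raise it. ALP that was high at entry and has not moved says little about a new liver event, yet it is enough to fail the definition.

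At stake is who is evaluated promptly as a potential Hy's law case and, on one reading, who is reported as an SAE on that ground. Confirmation, and with it the DLT criterion and mandatory discontinuation, starts from that evaluation. The planned tables would not reveal a missed case, because a per-test worst-grade summary cannot show ALT and bilirubin rising together in one patient.

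**Working it through.** The plan states no figure to reproduce. The check sets the Section 8.4.1 limits against the entry limits in criterion 8. All values are multiples of ULN, and hemolysis is assumed absent.

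**Entry range that fails the ALP condition.** The definition needs ALP <2. Criterion 8c allows up to 2.5, or up to 5 with bone or liver metastasis. The admitted values that fail are therefore 2.0 to 2.5 without such metastasis and 2.0 to 5.0 with it, for as long as ALP stays there.

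**Chosen cases.** These are illustrations, not trial data. Baseline ALT and TBili are normal except in case F.

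| Case | ALP, baseline to event | ALT / TBili at event | ALT and TBili limits met? | Full definition met? |
|---|---|---|---|---|
| A. Bone metastasis | 3, stable | 6 / 3 | yes (6 >3; 3 >2) | no (3 is not <2) |
| B. As A, ALP not available at event | 3, then none | 6 / 3 | yes | yes |
| C. | 1.9, stable | 10 / 3 | yes | yes |
| D. | 2.0, stable | 10 / 3 | yes | no |
| E. | 1.8 to 2.1 | 10 / 3 | yes | no |
| F. Liver metastasis, baseline ALT 4.0, TBili 1.2 | 4.0, stable | 12 / 3.5 | yes (see below) | no |

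Case A passes entry because 3 is at most 5. Cases A and B differ only in whether ALP was available: a missing value leaves the patient flagged, and a known unchanged value removes the flag. Cases C and D show the cut.

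Case F shows the asymmetry within one patient. The ALT limit is 2 x 4.0 = 8.0, which is above 3 and coincides with the alternative of >8, so it is >8.0. The TBili limit is 1.2 + 1.0 = 2.2, smaller than the alternative of >3. ALT 12 and TBili 3.5 exceed both adjusted limits, and the unadjusted ALP condition alone blocks the case. Liver metastasis is an obvious competing cause in case F, so case A is the cleaner illustration.

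**The case against.** **SAE reporting.** The SAE sentence names AST/ALT and TBili and does not mention ALP. It can fairly be read as not requiring the ALP condition, although its reference back to the definition points the other way. A reader might infer that these patients escape SAE reporting. The documents do not establish that; they leave it ambiguous.

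**Other safeguards.** A reader might also infer that such a patient would go unnoticed or continue dosing unchecked. That is not supported either, because several rules work without regard to ALP:

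- Section 8.4.1 asks for closer monitoring once transaminases pass 3 x ULN. It also says that "any case where uncertainty remains as to whether it represents a potential" Hy's law case should be reviewed with the sponsor.
- Table 3 withholds drug for related Grade 3 or 4 nonhematologic toxicity, and Section 5.4.3.3 restricts retreatment until recovery.
- Section 3.1.6 has Grade 3 or higher DLT rules.
- Sections 8.2.2 and 8.2.3 make abnormal tests AEs and important medical events SAEs under stated conditions.
- Under Section 8.1, "any non-serious AE that is determined by the sponsor to be serious will be reported" as an SAE by the sponsor.
- Section 9.7 has the safety review team look at individual data.

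These stand and limit the harm. They do not restore the missing flag. The sponsor-review clause completes a sentence about rises separated in time, and an ALP of 3 fails the condition outright rather than creating doubt. The DLT rules centre on the first 28-day cycle and excuse some isolated Grade 3 laboratory findings. After recovery, Table 3 lets Grade 3 toxicity resume at the same dose. The documents do not print the CTCAE cut-offs, so they do not show which grade case A would receive.

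**ALP as a discriminator.** A high ALP can point to disease or cholestasis. That is a fair argument for a rising ALP and a weak one for a value unchanged since entry.

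**The listing.** The SAP plans no joint liver display whatever the ALP rule says, so a listing could be called a reporting preference. It is still the only inexpensive way to see whether the ALP condition mattered in the data already collected.

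**Conclusion.** The gap is real but narrow. Under the Section 8.4.1 definition as written, a patient whose ALP stays at an admitted baseline of 2 x ULN or more is not flagged for evaluation as a potential Hy's law case, however far AST/ALT and TBili rise. This assumes that ALP is measured and does not fall below 2 x ULN. The range concerned is 2.0 to 2.5 x ULN at entry, or 2.0 to 5.0 x ULN with bone or liver metastasis. The documents do not give the number of patients in that range, or the number with a joint rise, so no frequency can be calculated.

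The conclusion covers the flag for evaluation. It does not extend to a claim that SAEs go unreported or that other safety rules fail. Severity is minor, and the change is a cheap improvement.

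**What to change.** **Main change, SAP Section 9.2.3.2.** List and count all treated patients who meet the AST/ALT and TBili limits, baseline-adjusted as in Section 8.4.1, regardless of ALP. Show baseline and concurrent ALP for each. Protocol Table 4 already collects ALP, AST, ALT and total bilirubin, so the cost is one listing. It covers existing data from every treated patient and would show all six cases above. If the SAP is not reopened, the listing can be reported in the CSR as an addition to the plan.

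**Secondary change, Protocol Section 8.4.1.** State that when baseline ALP is 2 x ULN or more, ALP alone does not exclude a potential case and is weighed in the etiology work-up. State also that this applies to the SAE-reporting paragraph, which removes the ambiguity there. Cases A, D and F would then be flagged. Case E, whose ALP first passes 2 x ULN on study, would not be, and is left to the listing and sponsor review.

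The secondary change has limited reach. The sponsor decided to terminate the study on 07 September 2022. The schedule following Amendment 9 has no laboratory rows, and after the primary completion date safety assessment follows local standard of care (Appendix 8). The wording would act only on locally ordered tests in patients still on treatment.

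The downside of both changes is a few extra work-ups or listed cases that prove to be disease-related.
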